10.5 Efficacy Analyses

The analysis for efficacy endpoints will utilize the efficacy analysis set. Subjects will be analyzed according to their randomized treatment groups in the parent study 20120295 **and the first dose received in the 20130255 OLE study.**

For primary analysis of efficacy endpoints summary statistics on observed data are provided by visit and treatment group. Subgroup analysis of the secondary efficacy endpoints on observed data will be provided by sex, race, region and medication overuse, and by visit and treatment group.

PROs include PROMIS Pain interference, migraine symptom interference items, MSQ, **MPFID** and MIDAS. Change from baseline in total score (or subscale if applicable) of each PRO will be summarized descriptively on observed data by visit and treatment group. No sensitivity analysis will be conducted for PROs.

10.6 Safety Analyses

For safety endpoints, including laboratory data, vital signs and other non-AE safety data, all enrolled subjects who received at least one dose of investigational product (ie, utilizing the SAS) will be analyzed based on the treatment received in

the 20130255 OLE study. Three treatment groups will be considered, based on planned dosing:

- 70 mg: including all subjects who receive 70 mg for at least 80% of the time exposed
- 140 mg: including all subjects who receive 140 mg for at least 80% of the time exposed
- 70/140 mg mix: including all subjects who receive any one dose <80% of the time exposed

A total AMG 334 group will also be presented in the tables.

For AE safety data two treatment groups will be considered:

- 70 mg
- 140 mg

A total AMG 334 group will also be presented in the tables.

No statistical testing comparing treatment groups will be performed in the safety analyses.

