4.1 Inclusion and Exclusion Criteria

4.1.1 Inclusion Criteria

- 101 Subject has provided informed consent prior to initiation of any study-specific activities/procedures
- 102 Completed the 12-week study visit and did not end IP early during the double-blind treatment period of the AMG 334 20120295 parent study, and is appropriate for continued treatment

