4.1.2 Exclusion Criteria

- 201 Development of any unstable or clinically significant medical condition, laboratory or ECG abnormality following randomization into the parent study, that in the opinion of the investigator, would pose a risk to subject safety or interfere with the study evaluation, procedures or completion

Note: Any ECG abnormality noted by the central reader must be evaluated by the investigator to determine if the ECG finding is representative of an unstable or clinically significant medical condition.
- 202 Any subject who experienced an SAE in the parent study (AMG 334 20120295) for whom the investigator determined that there was a reasonable possibility that the event may have been caused by investigational medicinal product
- 203 In the opinion of the investigator, subject demonstrated poorly controlled hypertension following randomization into the parent study
- 204 Systolic blood pressure (BP) 160 mm Hg and/or diastolic BP 100 mm Hg or greater at screening/Day 1

If the systolic BP is > 160 mm Hg or diastolic BP is > 100 mm Hg when initially assessed, BP may be repeated 30 minutes after the initial measurement. BP measurements may only be repeated once after the initial measurement
- 205 Subject is currently or plans to participate in another clinical study during participation in this study
- 206 Subject who used excluded concomitant medications between week 8 and week 12 of the parent study
- 207 Pregnant (as confirmed by the week 12 urine pregnancy test of parent study) or breastfeeding, or is a female expecting to conceive during the study, including through 16 weeks after the last dose of investigational product

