10.4 Planned Methods of Analysis

10.4.1 General Considerations

All subjects who have received at least one dose of AMG 334 in the study will be included in the data analysis according to their allocated treatment groups in the parent study, as well as an overall analysis (of all subjects in the OLE study).

For the purpose of primary analysis for secondary and exploratory endpoints in the 20130255 OLE study, baseline is defined as baseline of the AMG 334 20120295 parent study (from the first day subject used eDiary in baseline at week -4 study visit through the day prior to study day 1). However, change from the parent study Month 3 data will also be evaluated.

Descriptive statistics will be presented for all endpoints. Summary statistics for continuous variables will include number of subjects, mean, median, standard deviation,

standard error, lower and upper quartiles, minimum, and maximum. For categorical variables, frequency and percentage will be given.

No formal statistical tests will be performed. Missing values for safety endpoints will not be imputed.

Subject disposition, demographics, and baseline characteristics will be summarized.

The full analysis set will be utilized to tabulate subject disposition of all enrolled subjects, the demographic data, baseline disease characteristics, efficacy, and safety endpoints.

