6.1 Definition of Terms Included in Study Endpoints

6.1.1 Safety Endpoints

Serious Adverse Event (SAE)

SAEs determined by the flag indicating if the adverse event is serious on the Adverse Events (AE) eCRF page will include those that occur after signing of the informed consent and up to and including end of study.

Treatment-Emergent Adverse Event

Adverse Events (AEs) recorded on the Adverse Events eCRF page that occur on or after first dose of investigational product as determined by the flag indicating if the adverse event started prior to the first dose on the Adverse Events eCRF and up to and including 112 days after the end of investigational product (16 weeks after the last dose of IP) or end of study, whichever comes earlier.

An AE that started in parent study 20120295 is only considered treatment emergent in the OLE study 20130255 if there is a worsening of the event. If the event is ongoing with no changes in severity, then it will not be considered an AE in 20130255.

Treatment-Related Adverse Event

A treatment-related AE is defined as a treatment-emergent adverse event that is considered by investigators to have reasonable possibility that it may have been caused by IP as determined by the flag indicating if the event is caused by investigational product on the Adverse Events eCRF page.

Columbia-Suicide Severity Rating Scale (C-SSRS)

The C-SSRS is a clinician rating of suicidal behavior and ideation. The version "Since Last Visit" will be used for this study. The C-SSRS consists of a maximum of 20 items to evaluate suicidal behavior and suicidal ideation. Please refer to [Appendix B](#) for more details.

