9.4 Detection of Bias

As an open-label extension study, the potential bias introduced by selecting subjects, allocating treatment groups and assessing endpoints is minimal. However, it is recognized that the data of study 20130255 may suffer from a selection bias associated with dropout from the parent study 20120295. Other factors that may bias the results of the study include:

- important protocol deviations
- investigational product dosing non-compliance
- the timing of and reasons for early withdrawal from treatment and from study in 20130255

The incidence of these factors may be assessed. Important protocol deviations likely to impact the analysis and interpretation of the efficacy endpoints will be listed and/or tabulated in the clinical study report (CSR). If necessary, the incidence of other factors will be tabulated.

The timing of and reasons for early withdrawal from treatment and from study will be tabulated and/or listed. Ad-hoc analysis on time to early withdrawal from treatment and

from study may be performed according to the actual treatment received in the parent study 20120295 or the reasons of early withdrawal.

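### The AE tables cannot separate subjects starting AMG 334 from those continuing it, and the safety grouping differs between protocol and SAP without being recorded as a change

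*SAP*

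**What the plan says.** **Who enters.** Inclusion criterion 102 (Protocol 4.1.1) requires that the subject "Completed the 12-week study visit and did not end IP early during the double-blind treatment period of the AMG 334 20120295 parent study" and be suitable for further treatment. Exclusion criterion 202 (Protocol 4.1.2) removes "Any subject who experienced an SAE in the parent study (AMG 334 20120295) for whom the investigator determined that there was a reasonable possibility" of a causal link to the product. Criteria 201 and 203 remove subjects who, after parent randomisation, developed clinically significant conditions or abnormalities, or poorly controlled hypertension. Former placebo subjects enter as well: SAP 7.2 names placebo-origin groups for each extension dose.

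**How AEs are grouped.** SAP 10.6 states "For AE safety data two treatment groups will be considered", namely 70 mg and 140 mg, with a total. SAP 7.3 gives the same two groups, and SAP 10.6.1.1 assigns each event to the dose at onset. The AE window in SAP 6.4 opens after the first extension dose.

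**What the protocol promised.** Protocol 10.4.1 says that subjects are included "according to their allocated treatment groups in the parent study, as well as an overall analysis", and lists safety among the endpoints tabulated on the full analysis set. Protocol 10.4.3, the safety section, groups by the highest dose actually received and does not mention the parent arm.

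**What the SAP says about change and bias.** SAP Section 11 records a change of grouping for efficacy only. SAP 9.4 describes "the potential bias introduced by selecting subjects" as minimal, then acknowledges possible selection through dropout from the parent study.

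**The concern.** Two kinds of subject contribute to every AE table. For former AMG 334 subjects the entry criteria act on 12 weeks of experience with the drug, and those 12 weeks lie outside the extension's AE window. For former placebo subjects the criteria can say nothing about AMG 334, and their follow-up starts with the first dose. A 70 mg, 140 mg or total rate averages the two in proportions that no safety table shows. Disposition and baseline tables (SAP 10.2 and 10.4) are also by extension dose only.

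The rate after starting AMG 334 and the rate on continued treatment therefore cannot be recovered for the primary endpoint. This matters most for events that come early or lead to stopping. The SAP already uses the parent arm to group efficacy and pharmacokinetic data, but not AEs.

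**Working it through.** The plan gives no AE rate, parent allocation or figure on this point, so there is nothing to reproduce. The check compares the grouping rules and then illustrates what pooling can do.

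**1. Grouping rules for safety**

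| Source | Grouping |
|---|---|
| Protocol 10.4.1 | Parent-study arm, plus overall |
| Protocol 10.4.3 | Maximum actual extension dose |
| SAP 7.3, 10.6, 10.6.1.1 (AEs) | Extension dose at onset, plus total |
| SAP 11 (changes from protocol) | Efficacy grouping only |

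The two protocol rules are not reconciled, the SAP's AE rule is a third one, and Section 11 does not list it.

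**2. Effect of pooling on a rate**

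Let w be the drug-naive share of person-time, and r the event rate in previously exposed subjects divided by the rate in drug-naive subjects. Both are assumptions. Then

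pooled rate / drug-naive rate = w + (1 − w) × r

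| w | r = 0.25 | r = 0.5 | r = 0.75 | r = 1 | r = 1.25 |
|---|---|---|---|---|---|
| 0.25 | 0.438 | 0.625 | 0.813 | 1.000 | 1.188 |
| 1/3 | 0.500 | 0.667 | 0.833 | 1.000 | 1.167 |
| 0.50 | 0.625 | 0.750 | 0.875 | 1.000 | 1.125 |

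For example, 1/3 + (2/3) × 0.5 = 0.667. Pooling has no effect at r = 1, and the direction reverses above 1.

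**3. An early-onset event under the SAP's incidence definition** (subjects with the event divided by time to first event)

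Assume a 5% risk specific to the first 84 days of first exposure, a background rate of 2 per 100 subject-years for everyone, and 448 days of follow-up (64 weeks × 7). Here w is the drug-naive share of entrants.

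- Drug-naive: cumulative hazard = −ln(0.95) + 0.02 × 448/365.25 = 0.0513 + 0.0245 = 0.0758. The proportion with the event is 1 − exp(−0.0758) = 0.073. Time to first event averages about 1.157 years, so the rate is 6.3 per 100 subject-years.
- Previously exposed: 1 − exp(−0.0245) = 0.0242 over about 1.212 years, which gives 2.0.
- Pooled, w = 0.25: (0.25 × 0.073 + 0.75 × 0.0242) / (0.25 × 1.157 + 0.75 × 1.212) gives 3.0, a ratio of 0.48.
- Pooled, w = 0.50: 4.1, a ratio of 0.65.

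With a 10% early risk and a background rate of 5 per 100 subject-years, the rates are 14.2 (drug-naive), 5.0 (previously exposed) and 7.1 to 9.4 (pooled), with ratios of 0.50 to 0.66. Over 364 days the two scenarios together give 0.45 to 0.64.

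**The case against.** **Protocol 10.4.3 is the safety-specific section and contains no parent-arm split.** On this view the specific section governs. This stands in part. A reader might infer that the SAP removed a promised safety analysis, but the documents do not support so plain a reading. They show two protocol sections in conflict and a SAP that follows neither exactly and does not record its choice.

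**The criteria are the same for all arms and are applied while parent assignment is blinded (Protocol 6.2).** They also filter former placebo subjects on adherence and general proneness to AEs. Criteria 102 and 202 do not exclude a subject who had non-serious events and stayed on treatment, or one with an unrelated SAE. It would therefore be too strong to say that former AMG 334 entrants have all tolerated the drug. What remains is that only in the former AMG 334 arms can the filter act on the response to AMG 334.

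**The treatment-emergence rule.** Under SAP 6.1.1 an event that began in the parent study "is only considered treatment emergent in the OLE study 20130255 if there is a worsening of the event". It is tempting to count this as further selection. It is not: the rule decides which events count, selects no subjects, and applies equally to events that began on placebo.

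**The objective is long-term safety, no tests are planned, and first-exposure rates can come from the randomised parent study.** This stands as a reason to keep the pooled tables. However, the parent double-blind phase lasted 12 weeks. Within the extension, only the former placebo group is followed for about a year from its first dose.

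**SAP 9.4 does acknowledge selection through parent dropout** and allows ad hoc time-to-withdrawal analyses by parent treatment. These are optional and are not AE tables.

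**Conclusion.** The concern holds in a limited form. It is firm that no planned AE table separates first from continuing exposure, that Protocol 10.4.1 and 10.4.3 disagree, and that SAP Section 11 is silent on the safety grouping.

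The effect on reported rates is less certain. Pooled rates can understate the first-exposure rate for early-onset or intolerance events. A reader might infer that AE rates in general are diluted, perhaps by a quotable percentage. The documents do not support that, because they contain neither the parent allocation nor any event rates. The ratios of 0.48 to 0.66 rest on the assumed early risks, background rates and drug-naive shares of 0.25 to 0.50. Events that increase with cumulative exposure would shift the pooled rate the other way.

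The pooled analysis is not wrong for a long-term objective. What is missing is a supportive view that the primary endpoint needs in order to be interpreted.

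**What to change.** - **SAP 7.3 and 10.6.1:** keep the tables by extension dose and total. Add exposure-adjusted tables of all TEAEs, SAEs and AEs leading to withdrawal of IP by parent-study treatment: former placebo versus former AMG 334, plus total, within extension dose where numbers allow. This two-way split is coarser than the allocated arms in Protocol 10.4.1; showing placebo, 70 mg and 140 mg separately would follow that section literally. Label the tables descriptive, because entry follows post-randomisation selection.
- **Protocol 10.4.1 and 10.4.3:** reconcile the two grouping rules.
- **SAP 11:** list the safety grouping actually used for AEs as a change from the protocol.
- **SAP 9.4:** replace the statement that selection bias is minimal with one saying that the entry criteria pre-select former AMG 334 subjects on 12-week completion and absence of related SAEs. Do not attribute selection of subjects to the treatment-emergence rule.

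The cost is a few descriptive tables from data already held, since parent treatment is already used for efficacy. The groups are smaller. With no events observed, the 95% upper bound 1 − 0.05^(1/n) is 0.46% for 651 subjects, 0.92% for 325 (a half share) and 1.83% for 162 (a quarter share).

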10.6.1 Adverse Events and Disease Related Events

The Medical Dictionary for Regulatory Activities (MedDRA) version **18.0** or later will be used to code all events categorized as adverse events (AEs) to a system organ class and a preferred term (PT). **All adverse events will be graded using the Common Terminology Criteria for Adverse Events (CTCAE) Version 4.** Refer to [Section 6.1](#) for the definition of treatment-emergent adverse event.

Exposure-adjusted subject incidence of AEs will be summarized for all treatment-emergent AEs (TEAEs), serious AEs, AEs leading to withdrawal of investigational product, fatal AEs and treatment-related adverse events.

Exposure-adjusted subject incidence of all TEAEs, serious AEs, AEs leading to withdrawal of investigational product, serious AEs leading to withdrawal of investigational product and fatal AEs will be tabulated by system organ class and preferred term in alphabetical order.

In addition, exposure-adjusted subject incidence of all TEAEs and serious AEs will be tabulated by system organ class, preferred term and CTCAE grade in alphabetical order. Exposure-adjusted subject incidence of all TE AEs and serious AEs will also be tabulated by preferred term in descending order of frequency.

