7. STUDY PROCEDURES

7.1 Schedule of Assessments

Refer to the Schedule of Assessments ([Table 1](#)) for an outline of the procedures required at each study visit. Each study visit during the open-label treatment phase and the safety follow-up phase has a window of ± 4 consecutive calendar days. The day 1 visit should occur once a subject has completed all 12-week procedures of the parent

study and within 14 days of the 12-week visit of the parent study. The subject may not enroll in this study on the same day as the week 12 visit of the parent study as the investigator must review the week 12 laboratory data and the central read of the week 12 ECG prior to enrolling the subject in order to assess clinical significance of this data as per exclusion criteria.

All study procedures for a given study visit are to be completed on the same day.

Investigators are responsible for ensuring that all study procedures are performed as specified in the protocol.

Study visits should be conducted without additional non-protocol therapies and subjects should be reminded about the investigational nature of the study drug.

Refer to the applicable supplemental (eg, laboratory) manuals for detailed collection and handling procedures.

Table 1. Schedule of Assessments
General Assessments and Administrative Procedures

	Screening	Day 1 ^a	Wk 4 / M1	Wk 8 / M2	Wk 12 / M3	Wk 16 / M4	Wk 20 / M5	Wk 24 / M6	Wk 28 / M7	Wk 32 / M8	Wk 36 / M9	Wk 40 / M10	Wk 44 / M11	Wk 48 / M12	Wk 52 / M13 / ET	Wk 64/M16 (16 Wks/4M After Last Dose of IP)
Informed Consent	X															
Physical Examination															X	
Weight															X	X
Vital Signs	X ^b		X	X	X	X	X	X	X	X	X	X	X	X	X	X
ECG			X		X			X ^c			X ^d				X	
Concomitant Medications Recording		X	X	X	X	X	X	X	X	X	X	X	X	X	X	X
IP Administration		X	X	X	X	X	X	X	X	X	X	X	X	X		
SAE/AE Recording		X	X	X	X	X	X	X	X	X	X	X	X	X	X	X
Enrollment		X														
Calls to IVR/IWR System ^e	X	X	X	X	X	X	X	X	X	X	X	X	X	X	X	X
Subject Brings eDiary to Site	X	X	X	X	X			X				X			X	

Footnote defined on last page of the table

Table 1. Schedule of Assessments
Laboratory Procedures and Clinical Outcome Assessments

	Screening	Day 1 ^a	Wk 4 / M1	Wk 8 / M2	Wk 12 / M3	Wk 16 / M4	Wk 20 / M5	Wk 24 / M6	Wk 28 / M7	Wk 32 / M8	Wk 36 / M9	Wk 40 / M10	Wk 44 / M11	Wk 48 / M12	Wk 52 / M13 / ET	Wk 64/M16 (16 Wks/4M After Last Dose of IP)	
UDS	Testing as needed throughout study based on investigator's clinical suspicion																

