40	Week 36 dose date; study day 253 if week 36 dose is not received (either missed or IP discontinued prior to week 36)	Week 40 IP dose date-1; study day 280 if week 40 dose is not received (either missed or IP discontinued prior to week 40)
44	Week 40 dose date; study day 281 if week 40 dose is not received (either missed or IP discontinued prior to week 40)	Week 44 IP dose date-1; study day 308 if week 44 dose is not received (either missed or IP discontinued prior to week 44)
48	Week 44 dose date; study day 309 if week 44 dose is not received (either missed or IP discontinued prior to week 44)	Week 48 IP dose date-1; study day 336 if week 48 dose is not received (either missed or IP discontinued prior to week 48)
52	Week 48 dose date; study day 337 if week 48 dose is not received (either missed or IP discontinued prior to week 48)	Study day 364

Note: for the intervals in month 6, 10, and 13 all available data before the next planned IP dose or visit should be used for calculation. Also refer to the definition of Monthly Migraine Days in [Section 6.1.2](#).

Study Visit

Since the actual visit for a subject may not exactly coincide with his/her targeted visit date, the actual visit date is mapped to the study visit as follows (visit windows below only apply to visits other than safety follow-up visit):

Study Phase	Study Visit	Target Day	Study Day
Open-label Treatment Phase	Day 1	1	1
	Week 4	29	2-43
n = 2 to 13	Week 4n	28n+1	28n-12 to 28n+15
	Week 8	57	44-71
	Week 12	85	72-99
	Week 16	113	100-127
	Week 20	141	128-155
	Week 24	169	156-183
	Week 28	197	184-211
	Week 32	225	212-239
	Week 36	253	240-267
	Week 40	281	268-295
	Week 44	309	296-323
	Week 48	337	324-351
	Week 52	365	352-379
	Safety Follow-up	The nominal visit from RAVE	

Note: If more than one visit (including the unscheduled visits, ie, CPEVENT='UNSCHED') fall within the same defined window, **scheduled visit will be used regardless of the distance from the target day. Unscheduled visit will only be used when there is no scheduled visit in the defined window.** The closest visit to the target day **among the same type of visit (scheduled vs. unscheduled)** will be considered for analysis. If two assessment dates are equidistant from the target date, the latter visit will be considered for analysis.

Above study visit table will be used for lab, vital signs, C-SSRS and PROs collected during office visit.

For adverse event, analysis windows will be set up based on study phase:

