Study Phase	Start Time Point	End Time Point
Screening Phase for SAE only	Informed consent date	One study day prior to the first IP dose
Open-label Treatment Phase	Study Day 1 after the 1 st IP Dose	Min(EOS date, last IP dose date + 112 days)

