- **Change from baseline in pain interference with daily activities and migraine-specific impact, as measured by the PROMIS Pain Interference Scale short form and single pain and migraine symptom interference questions**
- **Change in physical impairment over time as measured by the MPFID**

- **Change in impact on everyday activities over time as measured by the MPFID**

Other endpoints

- change from baseline in monthly acute medication treatment in days
- change from baseline in monthly average migraine symptoms interference scale

Percent Change from Baseline

The change from baseline divided by baseline and multiplied by 100:

$$(\text{post-baseline} - \text{baseline}) * 100 / \text{baseline}$$

If the baseline value is 0, then the percent change from baseline is set to be missing. Percent change from baseline in monthly migraine days which is used to determine 50%, 75%, and 100% responder will be calculated as above.

Subject Incidence

The subject incidence for a given event in a given period is defined as the number of subjects with at least one reported occurrence of the event divided by the number of subjects who entered that period. For subjects with multiple occurrences of the same event, the event will only be counted once per subject.

Exposure-Adjusted Subject Incidence

The **exposure-adjusted subject incidence in a given period** is defined as the number of subjects with at least one reported occurrence of the event in a given time period of follow-up divided by total subject years of follow-up in that period. **For subjects with events, only the time until the first event contributes to the total subject years of follow-up. This rate will be presented per 100 subject years.** For subjects with multiple occurrences of the same event, the event will be only counted once per subject. Please refer to the table of safety analysis study windows in [Section 6.4](#) to calculate follow-up time in days for each subject.

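### The Total-column exposure-adjusted rate of AEs leading to withdrawal of IP counts up to 112 days after the last dose as time at risk, which makes it about 19% to 25% too low for a completer

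*SAP*

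**What the plan says.** SAP 6.6 defines exposure-adjusted subject incidence as the number of subjects with the event divided by total subject-years of follow-up, shown per 100 subject-years. Time is cut short in one case only: "For subjects with events, only the time until the first event contributes to the total subject years of follow-up". For the length of follow-up it directs the reader to SAP 6.4 ("Please refer to the table of safety analysis study windows in" that section).

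The open-label AE window in SAP 6.4 starts after the first dose on day 1 and ends at "Min(EOS date, last IP dose date + 112 days"). This matches the treatment-emergent definition in SAP 6.1.1, which runs "up to and including 112 days after the end of investigational product (16 weeks after the last dose of IP) or end of study".

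SAP 10.6.1 applies the rate to "serious AEs, AEs leading to withdrawal of investigational product, fatal AEs and treatment-related adverse events", and later to serious AEs leading to withdrawal of IP. Neither withdrawal outcome is given a different risk period.

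Two other time rules matter:
- SAP 6.6 defines the duration of IP exposure as ending at the earlier of 27 days after the last dose and end of study. It does not use this for the AE denominator.
- SAP 10.6.1.1 bases the rates by dose on time spent at the dose level. It does not say whether days after the last dose belong to that level. It also tabulates the combined doses without a separate end of follow-up, so the SAP 6.6 rule is the only one stated for the Total column.

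**The concern.** In a person-time rate, each day in the denominator should be a day on which the event could happen. After the last scheduled dose there is no further dose to withhold, and after IP has been stopped for another reason it cannot be stopped again. Those days lengthen the denominator and add essentially nothing to the numerator.

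The error has one direction: it lowers the reported rate. It also ties the rate to the length of post-treatment follow-up. Two groups with the same experience on treatment would show different rates if one were followed longer afterwards.

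Withdrawal because of AEs bears directly on the primary objective of safety and tolerability. For AEs, SAP 10.6.1 plans only exposure-adjusted incidence, so no unadjusted withdrawal-AE percentage is specified there beside the diluted rate.

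**Working it through.** **Inputs**
- Last scheduled dose: Week 48 (Protocol Table 1), nominally day 337. SAP 6.4 gives the start of the last interval as "Week 48 dose date; study day 337 if week 48 dose is not received".
- Window after the last dose: 112 days (SAP 6.1.1 and 6.4).
- Final visit: Week 64 (Protocol Table 1).
- End of IP exposure: last dose + 27 days (SAP 6.6), which is day 364 for a completer.

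**The plan's own figure.** 16 × 7 = 112 days, and 337 + 112 = 449. Week 64 is 28 × 16 + 1 = day 449. The window and the schedule agree.

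**Total column, completer.** If the event is rare, event-free subjects determine the denominator, so

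understatement = 1 − (days at risk) / (days counted).

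| Risk ends at | Days at risk | Days counted | Planned rate too low by | Corrected / planned |
|---|---|---|---|---|
| Last dose + 27 days | 364 | 449 | 18.9% | 1.23 |
| Last dose | 337 | 449 | 24.9% | 1.33 |

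Shifting the last dose by the ±4-day visit window changes these figures by less than half a percentage point.

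**Illustration (assumed event rate).** Take 651 completers, of whom 5% (32.55) have the event at day 168. Planned subject-years are (618.45 × 449 + 32.55 × 168) / 365.25 = 775.2, which gives 4.20 per 100 subject-years. With 364 in place of 449 the rate is 5.16, and with 337 it is 5.56.

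**All subjects (assumptions, not in the documents).** Suppose 20% stop IP early, with last doses spread evenly over the 12 earlier dosing visits (mean day 155).
- All are followed for 112 days: counted time is 0.8 × 449 + 0.2 × 267 = 412.6 days. Time to the last dose is 0.8 × 337 + 0.2 × 155 = 300.6, and 27 days later 327.6. The understatement is 27.1% or 20.6%.
- Early stoppers leave the study 27 days after their last dose: counted time is 0.8 × 449 + 0.2 × 182 = 395.6 days. The understatement is 24.0% or 17.2%.

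**Dose columns, two readings of SAP 10.6.1.1**
- Time at a dose level means the SAP 6.6 exposure duration: a completer on one dose is understated by at most 1 − 337/364 = 7.4%.
- Days after the last dose go to the last dose level: a subject who switches carries none of them at 70 mg (0%). At 140 mg, a Week 4 switch gives 1 − 336/421 = 20.2% to 1 − 309/421 = 26.6%. A Week 28 switch gives 1 − 168/253 = 33.6% to 1 − 141/253 = 44.3%. SAP 11 expects most subjects to receive both doses.

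**Last-dose date.** Protocol Table 1 marks no IP administration at Week 52. The Clinical Home Use footnote for Day 85, equated with Week 24 or Week 52, describes dosing by site staff. If a day-365 dose were given and end of study stayed at day 449, ending risk at that dose would give 1 − 365/449 = 18.7%.

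**The case against.** The strongest reply is that little depends on this rate. The study is a single-arm estimation study without hypothesis tests, interim analyses carry no stopping rules, and the denominator is openly described as follow-up. The number of subjects with a withdrawal AE does not change. The disposition tables (SAP 10.2) report withdrawals from IP with reasons, and SAP 9.4 provides for tabulating or listing their timing. All of this stands, and it lowers the severity. It does not make the denominator right for these outcomes.

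The second reply is that the end of risk is debatable. SAP 6.5 ties completion of treatment to the Week 52 assessment and the end-of-IP form, and SAP 6.6 counts exposure to 27 days after the last dose. Day 364 is therefore as defensible as day 337. This also stands, and is why the result is given as two figures.

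A reader might infer more than the documents support:
- **That the understatement reaches 27% overall.** That needs roughly one subject in five stopping early and all of them followed for 112 days. With shorter follow-up after stopping, the figure can instead fall to about 17%.
- **That one range applies to every column.** The dose columns have their own, ambiguous denominator.
- **That no event is possible after any subject's last dose.** In an early stopper, an AE between the last dose given and the next planned dose can still cause withdrawal.
- **That the study's main tolerability measure is wrong.** The primary endpoint is subject incidence of AEs, and no document gives the withdrawal-AE rate that status.

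**Conclusion.** The concern holds for the Total AMG 334 column. For AEs and serious AEs leading to withdrawal of IP, the planned denominator includes up to 112 days per subject in which the event essentially cannot occur. From the documents' own days, a completer's rate is 18.9% too low if risk ends 27 days after the last dose and 24.9% too low if it ends at the last dose. This rests on the event being rare, the last dose falling at Week 48 and follow-up running to Week 64.

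The size for all subjects cannot be fixed, because the documents give neither the early-stopping rate nor the length of follow-up after stopping. In the dose columns the effect ranges from at most about 7% for a single-dose completer to a distortion that falls mainly on 140 mg, depending on the reading of SAP 10.6.1.1.

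This is a should-fix. The 112-day window remains appropriate for the other AE tables.

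**What to change.** 1. In SAP 6.6 and 10.6.1, state that for AEs and serious AEs leading to withdrawal of IP, time at risk ends at the first of: the event; the end-of-IP decision date (defined in SAP 6.2); end of study; and, for subjects who received all planned doses, one pre-stated end point. That end point is either the last dose date or, to match the exposure duration in SAP 6.6, 27 days after it.
2. Count in the numerator only events within the same window, and list any AE flagged as leading to withdrawal with onset after it.
3. In SAP 10.6.1.1, use the same end point for the dose-level denominators of these two outcomes, and state how days after the last dose are assigned to a dose level.
4. Keep the 112-day window for all other AE tables.
5. Reconcile Protocol Table 1 with the Clinical Home Use Day 85 footnote on IP administration at Week 52, because they affect the last-dose date.

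The cost is a short SAP amendment, ideally before database lock, and one extra censoring date built from dates already collected. No new data are needed. The reported withdrawal-AE rate becomes somewhat less favourable.
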